Our own team conducted a pilot, phase 2/3 cluster-randomized clinical trial on the safety and efficacy of repeated IVM MDA in Burkina Faso (RIMDAMAL trial; NCT02509481) in 2015. We enrolled 8 villages (2712 participants) and administered 6 rounds IVM MDA to 4 randomized intervention arm villages, every 3 weeks, from late July through late November (control arm villages received only the first IVM MDA, as per standard policy for LF elimination ongoing at the study site). IVM, as per label guidelines, was only administered to individuals whose height was  $\geq 90\text{cm}$ . Our primary outcome was cumulative incidence of clinical malaria episodes in children  $\leq 5$  years of age. Active surveillance by trained nurses was performed 3 times every 2 weeks, and rapid diagnostic test (RDT)-positive malaria episodes were immediately treated with AL. The results showed that approximately 500 cases of malaria were averted per 1000 intervention arm children over the 18 week study (malaria incidence intervention arm=2.00, control arm=2.49, risk ratio=0.80 [0.70-0.91],  $P=0.0009$ ). The safety outcome from this trial was the number and type of adverse events (AE) recorded in the enrolled populace (2712 participants). The risk of AE was not noticeably different among participants of the intervention arm (3.1% of participants [45/1447]) vs. the control arm (1.9% of participants [24/1265]); risk ratio = 1.63 [1.01-2.67],  $P = 0.06$ . Most AE (85%; 55/65) were classified as "not related" to the intervention, while 5 were classified as "unlikely related", 1 as "possibly related", 7 as "probably related", and 1 was unclassified. Of the "possibly" and "probably" intervention-related AE, all were sub-classified as adverse reactions of mild or moderate intensity that consisted of vomiting, pruritus, edema in the limbs, or tremors, and all were monitored until resolved or given standard treatment as outlined by WHO guidelines(29). 20 deaths were recorded over the study period, all classified as either "unlikely" or "not related" to the intervention. The risk of AE between arms among all participants was similar, as was the risk of AE among the child cohort. The proportions of each sub-class of AE, the graded intensity category, or the outcomes did not differ between the arms. In total, these data suggest that administering repeated IVM to entire villages does not increase harms in the populace.

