A study nurse will be assigned to each village to work with the village CHWs to distribute the study drugs and LLINs. LLINs and SMC/IPTp drugs will be health services provided by the Burkina Faso MoH NMCP. Generic IVM and placebo will be purchased through the study from Laboratorio Elea or another provider. Malaria episodes in enrolled study village children  $\leq 10$  years of old will be determined by active case surveillance via study nurses visiting each child weekly with the CHW during the intervention to monitor for malaria episodes. An uncomplicated malaria episode will be defined as axillary temperature  $\geq 37.5$  °C (with adjustment for temperature taken at other locations) and/or history of fever in the last 24 hours, and a positive RDT for *Plasmodium* spp. Complicated malaria is defined in Appendix D. As per MoH guidelines, a standard course of AL will be administered to all children with uncomplicated malaria cases, while complicated malaria cases will be referred to the nearest district hospital to for treatment with either intravenous quinine or artesunate. Blood will also be preserved on slides and filter papers for later analysis. The nurse will record positive malaria episodes in children, as well as any spontaneously-reported AEs communicated by the study populace, into CRFs and treat them as able or refer them to the district hospital. Throughout the intervention phase, entomology teams will capture mosquitoes from intervention and control clusters, and parasitology teams will sample blood from selected study villagers along transects and at cross-section.

The intervention phase will be completed one month following the 8th SMC/IVM MDA round at the end of the 2nd rainy season, and the clinical component of the trial will be closed. Limited cross-sectional mosquito and blood sampling will occur in study villages in the 3rd rainy season, after the intervention is complete, to analyze any potential changes in mosquito or parasite populations in the villages. The blood sampling schedule is in table 4.

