## 5.3. Treatment Assignment Procedures

### 5.3.1. Randomization Procedures

This will be a cluster (village)-randomized trial. Once the chiefs/leaders and heads-of-households of all fourteen selected villages give their verbal consent to participate following informational and question and answer meetings with the study team, a village representative and the CHWs representing each village will be asked to participate in a public randomization event at the facilities of the district health authority, attended by the district medical director and members of the study team. In front of the attendees, the numbers “1” and “2” will be written on 7 cards each, which will be sealed in identical opaque envelopes, mixed in a container, and then randomly pulled from the container by each village representative. Villages will be assigned to the arm written on the card selected by this representative, and the procedures will be video recorded. These arm designations will be linked to the masked active ingredient tablet or placebo (below).

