## 10. STATISTICAL CONSIDERATIONS

### 10.1. Study Hypotheses

The primary objective hypothesis is that repeated IVM MDAs (the intervention) coinciding with SMC rounds and other standard-of-care malaria control measures (LLIN distribution, IPTp) will significantly reduce the incidence of childhood malaria compared to the placebo intervention. This hypothesis will be tested in a 2-arm superiority trial with a cluster randomized design. The primary outcome measures of incidence of malaria episodes among village children ≤ 10 years of age in each arm will be used to test the hypothesis. The primary objective null hypothesis is that that repeated IVM MDAs coinciding with SMC rounds and other standard-of-care malaria control measures will have no effect on the incidence of childhood malaria compared to placebo MDAs coinciding with SMC rounds and other standard-of-care malaria control measures.

Secondary objective hypotheses:

- The risk of adverse events (AEs) per participant in the intervention arm occurring over the intervention phase of the trial will not differ relative to the risk of adverse events in the control arm.  
*Null: The risk of adverse events (AEs) per participant in the intervention arm occurring over the intervention phase of the trial will not differ relative to the risk of adverse events in the control arm.*
- The survival rates of wild blood fed *Anopheles gambiae* s.l. will be significantly reduced, and age-structure and entomological inoculation rate in wild *Anopheles gambiae* s.l. significantly younger/lower, in those captured from intervention arm villages as compared to those captured control arm villages at equivalent time intervals during the intervention phase. Also, the immuno-reactivity of intervention-arm participants' IgG over time to an *Anopheles* salivary gland peptide will be significantly lower than that from control arm participants.  
*Null: The survival rates of wild blood fed Anopheles gambiae s.l., and parity and sporozoite rates in wild Anopheles gambiae s.l., will not differ in those captured from intervention arm villages as compared to those captured control arm villages at equivalent time intervals during the intervention phase. Similarly, the immuno-reactivity of intervention-arm participants' IgG over time to an Anopheles salivary gland peptide will be no different than that from control arm participants.*

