1. OVERVIEW OF THE STATISTICAL DESIGN FOR RIMDAMAL II

- 1.1 Design overview: RIMDAMAL II is a double-blind cluster randomized controlled trial of repeated ivermectin (IVM) mass drug administration (MDA) in addition to standard malaria control (SMC) for integrated control of malaria. The primary hypothesis is that repeated IVM MDAs coinciding with SMC rounds and distribution of long-lasting insecticidal nets (the intervention) will significantly reduce the cumulative incidence of malaria in children ≤ 10 years of age compared to SMC and long-lasting insecticidal nets (LLIN) alone. The primary objective is to determine the efficacy of adding seasonal ivermectin mass drug administrations (IVM MDA) to the standard-policy malaria control measures in the Sahel (SMC in children, LLIN coverage, IPTp in pregnant women), for reducing the incidence of uncomplicated malaria episodes in enrolled village children (≤ 10 years of age) assessed by active case surveillance. IVM or placebo MDA will be given monthly over 4 months of the rainy season to the eligible village population, each as 3-day course of 300 μg/kg/day for two consecutive years.
- **1.2 Study population:** The RIMDAMAL II study population is comprised of fourteen spatially-delineated villages in southwest Burkina Faso, equally divided between placebo and IVM. Villagers are indigenous Burkinabé from various ethnic groups, most of whom farm and rear livestock. The village population sizes range between approximately 150-450 people with approximately 100 children between 0-10 years old in each village.

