2. ANALYSIS PLAN

2.1 Primary analysis

The primary outcome will be analyzed as intention-to-treat (ITT). The number of episodes per week among the active case detection (ACD) cohort (children age ≤ 10 years) will be used as the primary measurable outcome to evaluate the impact of the intervention when compared to the control arm. The active case detection cohort includes all enrolled children regardless of

eligibility or receipt of MDA or SMC. A mixed effects regression analysis with Poisson distribution will be used to assess the impact. The primary analysis will include a random effect for cluster (village), and 3 fixed effects (treatment effect, year, and sex; all binary covariates, no interactions evaluated). Subgroup analyses will include an evaluation of fixed effects such as LLIN use, age, and treatment with SMC or IVM. Estimates for the intervention effect from the primary analysis as well as subgroup analyses will be reported along with 95% confidence intervals. The statistical program SAS v9.4 (SAS Institute Inc., Cary, NC) will be used for primary statistical analyses. Secondary data generated from Aim 1 will include adverse events (AE), severe adverse events (SAE), and their relationship to the intervention/placebo. The risk of SAE and AE will be compared between intervention and control arms by calculating risks ratios and attributable risks with 95% confidence intervals.

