2.2 Secondary endpoints

- **2.2.1** Adverse events analysis: Safety is a secondary endpoint and will be assessed by relative risk (RR).
 - a. Groups
 - All participants_will be followed actively and passively for adverse events and the Risk Ratios (RR) of AEs in those in the intervention versus control clusters will be compared.
 - ii. Active Case Detection Cohort

- SMC-treated children only children age 3-59 months who receive SMC. RR of AEs in children who receive SMC and live in IVM-treated clusters versus those who receive SMC and live in placebo-treated clusters
- 2. **IVM/placebo-treated only** children ≥90cm and eligible for MDA/placebo. RR of AEs in those children receiving MDA versus those receiving placebo.
- iii. **Non-ACD participants** that were enrolled in the study were actively followed in the study on the days of study intervention through 24-hours post study intervention, and then passively for the rest of the MDA round.
- b. **Type** AEs will be further classified by seriousness, severity, relationship to the intervention, outcome, and organ system.
 - i. Classification (AE, SAE, etc)

Adverse Event: (ICH) E6 defines an AE as any untoward medical occurrence in a patient or clinical investigation subject administered a pharmaceutical product regardless of its causal relationship to the study treatment. FDA defines an AE as any untoward medical occurrence associated with the use of a drug in humans, whether or not considered drug related. An AE can therefore be any unfavorable and unintended sign (including an abnormal laboratory finding), symptom, or disease temporally associated with the use of a medicinal product.

Serious AE (SAE): An AE is considered "serious" if, in the view of either the site principal investigator or sponsor, it results in any of the following outcomes:

- 1. Death.
- 2. A life-threatening AE: An AE is considered "life-threatening" if, in the view of either the site principal investigator or sponsor, its occurrence places the patient or subject at immediate risk of death. It does not include an AE that, had it occurred in a more severe form, might have caused death.
- 3. Inpatient hospitalization or prolongation of existing hospitalization.
- 4. A persistent or significant incapacity or substantial disruption of the ability to conduct normal life functions, or
- 5. A congenital anomaly/birth defect.

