- Molecular force of infection (mFOI; also sometimes further subclassified as molFOB (molecular force of blood stage infection). Defined as the number of new *Plasmodium* clones acquired over time (count data). Will be determined using monthly filter paper samples in ACD children only.

An approach consistent with the primary analysis will be adopted here with both unadjusted and adjusted regression models. For parasite prevalence, a binomial regression model will be used, and for MOI and mFOI, Poisson and Negative Binomial regression model will be used, with the final model choice being indicated by the distribution of the dependent variable.

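### The SAP's adverse-event risk ratios and confidence intervals carry no stated allowance for village clustering or for having only 14 villages

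*SAP*

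**What the plan says.** The unit of randomisation is clear. Protocol 5.3.1 states "This will be a cluster (village)-randomized trial", and SAP 1.2 describes "fourteen spatially-delineated villages in southwest Burkina Faso, equally divided between placebo and IVM".

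For the primary endpoint, SAP 2.1 and 2.1.3 specify a Poisson mixed model with a village random effect and Kenward-Roger degrees of freedom, the latter because clusters are few. For parasite prevalence, multiplicity and force of infection, SAP 2.2.2 adds: "An approach consistent with the primary analysis will be adopted here". That sentence sits inside 2.2.2 and does not reach the safety section, 2.2.1.

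For safety, SAP 2.1 says that SAE and AE risk "will be compared between intervention and control arms by calculating risks ratios and attributable risks with 95% confidence intervals". SAP 2.2.1 repeats the risk ratio for all participants and for two groups of cohort children (SMC-treated, and IVM/placebo-treated), without mentioning intervals. Protocol 4 words the final comparison in the same way. Protocol 10.3.1 describes the same measures for the interim safety reviews and leaves the statistical techniques to a DSMB charter that is not among the documents.

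On ascertainment, protocol 4 says "A study nurse will be assigned to each village". Protocol 8.3 has AEs reach the nurses partly by spontaneous report, directly or through the village health worker.

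**The concern.** Harm is the first secondary objective and half of the benefit-risk argument. When villages are randomised, people in one village share an environment, a nurse and a reporting channel. The information about the arm contrast then comes from 14 units, not from about 4,700 people. An interval computed from individual counts is too narrow whenever AE risk or AE reporting differs between villages. It can signal harm that is not there, or rule out a harm that the data cannot exclude.

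The SAP recognises this for two other groups of endpoints, so its silence on safety stands out. Interval width also matters more than usual here. The safety hypothesis in protocol 10.1 is that AE risk in the intervention arm "will not differ relative to the risk of adverse events in the control arm", which is identical to the null printed beneath it. A non-significant ratio therefore has no defined interpretation, and the weight falls on the interval.

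**Working it through.** **1. What the earlier trial's AE result reproduces as.** The documents give no precision figure for this trial's safety comparison. The nearest figure is the earlier trial's result in protocol 2.1: 45/1447 v 24/1265 in 8 villages, risk ratio 1.63 [1.01-2.67], P = 0.06. As a plain 2×2 table:

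- RR = (45/1447)/(24/1265) = 0.03110/0.01897 = 1.64
- SE(log RR) = √(1/45 − 1/1447 + 1/24 − 1/1265) = 0.250
- 95% CI = exp(0.494 ± 1.96 × 0.250) = 1.00 to 2.67 (score interval 1.01 to 2.66)
- Chi-square with Yates correction: P = 0.060

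The match is close but not exact. The result shows no visible allowance for clustering.

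**2. Inputs for this trial.**

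- Village size m: 4,700/14 ≈ 336 (protocol summary). The other stated total, 5,000, gives 357.
- Between-village CV k: 0.258 (protocol 10.2, for malaria) and 0.2 (the January 2019 revision). Protocol 10.2 labels the 0.2 an intra-cluster coefficient. I read it as a CV because protocol 4 uses that label for 0.258, which 10.2 defines as a CV. Applying either value to AEs is an assumption.
- AE risk p: 2.5% to 3%, from the earlier trial's 1.9% and 3.1%.

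**3. Design effect.** ICC = k²p/(1 − p) and DE = 1 + (m − 1) × ICC, with m = 336.

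| k | p | ICC | DE | SE too small by | Null trials whose naive 95% CI excludes 1 |
|---|---|---|---|---|---|
| 0.2 | 2.5% | 0.0010 | 1.34 | 1.16 | 9% |
| 0.2 | 3% | 0.0012 | 1.41 | 1.19 | 10% |
| 0.258 | 2.5% | 0.0017 | 1.57 | 1.25 | 12% |
| 0.258 | 3% | 0.0021 | 1.69 | 1.30 | 13% |

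The last column is 2[1 − Φ(1.96/√DE)]. For the last row, 1.96/1.30 = 1.51, which gives 13%. A simulation of 20,000 null trials (7 v 7 villages of 336, 3% risk) agrees: 10% at k = 0.2 and 13% at k = 0.258. A village-level t-test stays near 5%. With m = 357 the design effects run from 1.37 to 1.73.

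**4. Effect on an interval.** Take the earlier trial's risks (3.11% v 1.90%) in 4,700 people.

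- Plain: SE(log RR) = 0.188, CI 1.13 to 2.37.
- ICC 0.001: DE 1.33. On t with 12 df (14 villages − 2; critical value 2.18), CI 1.02 to 2.63.
- ICC 0.002: DE 1.67, CI = exp(0.494 ± 2.18 × 0.188 × 1.29) = 0.97 to 2.78.

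Within the range implied by the plan's own CVs, the interval can move from excluding 1 to including it.

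**5. Sensitivity (assumed inputs).** With k = 0.258 and 10% risk, DE = 3.5 and the naive interval excludes 1 in about 29% of null trials. With k = 0.5 and 3% risk, DE = 3.6 and the figure is about 30%.

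**6. Rare SAEs.** At an assumed 0.1% risk, k of 0.2 to 0.258 gives DE of 1.01 to 1.02. The correct interval is about 1.1 times as wide, nearly all of it from using 12 df (2.18/1.96 = 1.11).

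**The case against.** The strongest reply is that the SAP names effect measures, not a variance method. A risk ratio with a 95% interval can come from a clustered model, so nothing in the text commits the analysts to an individual-level analysis. That is right. A reader might infer that participants will be analysed as if individually randomised, but the documents do not say so. The earlier trial's AE result makes the inference plausible and no more: it is another trial, its methods are not given here, and the match is only close.

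A reader might also infer that AE reporting depends strongly on village. The documents offer a mechanism but no data on AE variation between villages. Part of the assessment is shared across villages: the field physician judges seriousness, intensity and causality (protocol 7.9), and final grading is by consultation (protocol 8.2).

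It is also fair that the malaria CVs are borrowed, that larger distortions need assumed inputs, and that the unseen DSMB charter may settle the interim method.

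What remains is that a pre-specified plan for 14 randomised villages gives a cluster method to some endpoints and none to safety. Carried out as written, it permits an interval that is too narrow.

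**Conclusion.** The point holds as a gap in specification with a predictable direction of error. SAP 2.1 and 2.2.1 make no allowance for village clustering or for the small number of villages in the AE and SAE comparisons, and no other section extends one to them.

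The size cannot be fixed from the documents. If the malaria CVs carried over to AEs at about 3% risk, standard errors would be about 1.2 to 1.3 times too small, and the false-exclusion rate 10% to 13% instead of 5%. It would be worse with higher AE risk, which is conceivable because cohort children are questioned weekly over two seasons, or with greater variation between villages. Both are assumptions. For SAEs at around 0.1% the effect of clustering is slight, and the issue there is choosing a method that works with few events.

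The primary efficacy analysis is not affected.

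**What to change.** In SAP 2.1 and 2.2.1, state that AE risk ratios and risk differences, overall and in each listed subgroup, are estimated by a cluster-aware method with a small-sample correction. Two suitable choices are a mixed model with a village random intercept and Kenward-Roger degrees of freedom, or village-level risks compared on 12 df. Choose one in advance.

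For SAEs and other sparse events, name a village-level permutation or exact method, because log-risks are undefined in a village with no events. The card draw in protocol 5.3.1 makes all C(14,7) = 3,432 allocations equally likely, so a two-sided permutation P-value can go as low as 2/3,432 = 0.0006.

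Use the same method wherever DSMB tables compare arms, and refer to it in the charter.

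As a secondary correction, replace the safety hypothesis in protocol 10.1, now identical to its null, with an estimation statement: the AE risk ratio and difference will be reported with cluster-adjusted 95% intervals and interpreted from their limits.

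The cost is SAP and protocol wording and a few lines of code, with no new data. The price is wider safety intervals.

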2.1.1 Definition of analysis populations

Primary incidence analysis – We will use ITT analysis method for our prospective randomized trial and the population for the primary incidence outcome will be all enrolled children aged 10 years and younger.

Secondary safety analysis – Safety is being assessed with active and passive surveillance of all enrolled study participants, regardless of age. AEs will be further categorized by their relationship to the intervention and as SAEs based on their severity.

2.1.2 Definition of primary efficacy endpoint

A malaria episode is defined as the presence of a temperature of ≥37·5°C and/or history of fever in the last 24 hours, along with a positive rapid diagnostic test (RDT) for *Plasmodium* species (any species).

A participant's time-at-risk will be considered as censored for 14 days following a diagnosis and treatment of malaria due to the impacts of treatment on risk of recurrent malaria. Person time will be defined in 7-day consecutive intervals, with one or more visits occurring during this time considered as an eligible person-week.

Eligibility for MDA is determined at the beginning of each intervention season and is retained for the remainder of that season.

- Newborns are eligible for inclusion and will be considered exposed beginning at the time of their 1st ACD visit.
- Children who turn 11 years of age during an intervention season will remain eligible for the ACD cohort for the remainder of that season.
- If a participant ages out of ACD cohort in the first season, they will not be eligible for the ACD cohort in the second season.
- Eligibility for SMC is determined by the MoH community workers, not by the RIMDAMAL II study team. Participants may age out of SMC (>59 months) in the 1st season and become eligible for MDA (≥90 cm and >59 months) in the second season. They will not become eligible for MDA during the season where this occurred.

